#### **6.3 COMPLIANCE**

At each study visit, all study drug returned by the subject (used and unused) will be collected and new study drug will be dispensed as needed. The appropriate study personnel must document the number of used and unused ampoules. To accommodate Sponsor-approved telemedicine visits, study drug and device supplies will be allowed to be shipped directly to the subject.

Subject compliance with the prescribed dosage regimen will be monitored throughout the study. At each study visit, the subject will be asked whether they have been compliant with dosing instructions. If it is determined that a subject is noncompliant with study drug, the site personnel must re-educate the subject on proper dosing compliance and its importance. Continued noncompliance may lead to withdrawal of the subject from the study, after consultation between the Investigator and the Sponsor's Medical Monitor or other Sponsor representative.

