#### 7.5 EARLY TERMINATION VISIT

If the subject permanently discontinues study drug prior to Study Week 25 in the **Original Crossover Design**, or if applicable, Study Week 12 in the **Contingent Parallel Design**, for any reason, the subject should be encouraged to remain in the study and complete all visits up to and including the ET Visit.

If a decision is made to terminate a subject early from the study, the following assessments should be conducted as soon as possible and prior to study drug discontinuation, if possible:

- QOL questionnaires: SGRQ and UCSD SOBQ
- DE
- Vital signs: weight, RR, HR, and BP (following at least 5 minutes of seated rest and collected prior to 6MWT); no other measurements or procedures should be performed during the rest period

- 12-lead ECG (following at least 5 minutes of rest)
- Blood draws for clinical laboratory parameters and NT-proBNP (NT-proBNP sample must be drawn prior to 6MWT)
- Serum pregnancy test for females of childbearing potential
- •
- •
- •
- 6MWT (if possible, to be conducted between 10 to 60 minutes after the most recent dose of study drug and following at least 10 minutes of seated rest) and, if applicable, documentation of supplemental oxygen requirement
- Pulse oximetry (performed continuously prior to, during, and following the 6MWT)
- Borg dyspnea score immediately following the 6MWT
- PFTs (performed before the 6MWT or after recovery from the 6MWT)
- Confirm capture of actigraphy data
- Confirm capture of spirometry data
- Confirm capture of PGA data
- Verify study drug/device accountability
- Assess for AEs
- Assess for changes in concomitant medications

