#### 8 STUDY TERMINATION

#### 8.1 CRITERIA FOR SUBJECT WITHDRAWAL

Investigators and site staff should encourage subjects to continue participation in the study and complete all study procedures and study visits as indicated by the study protocol, unless subjects provide written withdrawal of consent from the study.

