# 8.1.1 Criteria for Withdrawal from Study Drug

Subject discontinuation from study drug does not mean discontinuation from the study. Subjects may voluntarily withdraw from study drug for any reason or the study drug may be withdrawn by the Investigator to protect subject safety. If a subject is withdrawn from study drug, the subject will be encouraged to actively continue to return for all study visits per the study protocol

and the Investigator will continue all reasonable efforts to obtain subject data. The primary reason for withdrawal from study drug should be documented in the subject's eCRF. If a subject discontinues study drug prematurely due to an AE, the subject will be followed until either the Investigator determines that the AE has resolved, it is no longer considered clinically significant, the subject is lost to follow up, or for 30 days if the AE extends beyond the final visit. If a subject discontinues study drug prematurely due to an SAE, the subject should be followed until resolution, death, or the subject is lost to follow-up, even if they are ongoing more than 30 days after completion of the final visit.

A positive pregnancy test will result in subject withdrawal from study drug, but the subject will be encouraged to continue participation in the study and complete all study visits. See Section 9.4.2 for information related to the reporting and following of pregnancies.

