7 GENERAL CONSIDERATIONS FOR DATA ANALYSES

Given the crossover design utilized for this study, efficacy and safety summary tables will follow the general format that baseline and post-baseline data will be presented by the assigned treatment condition when those data are observed during the treatment period. Treatments will be labeled as “Treprostinil” and “Placebo” to correspond with the assigned treatment condition.

Any efficacy and safety data that are collected during the washout period between Periods 1 and 2 will be presented for the assigned treatment condition from Period 1. Any follow-up data collected after Period 2, while on this study, will be assigned to Period 2. Subjects who are not retained will not be replaced during the study.

For continuous variables, the summary statistics will include the mean, standard deviation, median, lower quartile, upper quartile, minimum, and maximum. Statistics will be expressed using the level of precision in which the variable was collected. For discrete variables, summaries will include the frequency and percent in each category. Whenever practical, categories of discrete variables will be ordered and labeled as they appear in the case report form (CRF), and all categories represented on the CRF will be included in summaries, even when they do not apply to any patients in the study.

For data collected on a fixed schedule, the nominal time point will be used for summarization. Evaluations from Unscheduled Visits are to be mapped to Scheduled Visits to the extent possible per the protocol-specified windows. Repeat or redundant observations within an assessment window and observations that do not fall within any predefined assessment window will be excluded from summaries. If an evaluation is repeated, such as to confirm an observed aberrant laboratory value, the analyses will use the later value if within the protocol-specified window.

Unless otherwise specified, all final statistical tests will be 2-sided at alpha level 0.05 if the interim analysis is not conducted, and 0.022, if conducted. All tables will be presented in landscape format. For practical reasons, the point size may be reduced to (but not less than) 7 point for tables that contain too much information to fit into a single page. SAS[®] version 9.4 or higher will be used. The Sponsor's Biostatistics Department will analyze the efficacy and safety data.

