7.6 PREMATURE DISCONTINUATION AND MISSING DATA

Investigators and site staff are to encourage all subjects to continue their participation in the study and complete all study procedures and study visits as indicated by the study protocol unless the subject provides a written withdrawal of consent from the study. A subject's discontinuation from study drug does not mean discontinuation from the study. If study drug is discontinued for a randomized subject, the subject will be encouraged to actively continue to

return for all study visits per the study protocol, and the Investigator will continue all reasonable efforts to obtain the subject's data.

Patients may not complete the full treatment periods for the following reasons: death, lost to follow-up, study terminated by Sponsor, COVID-19 truncation, or withdrawal of consent. All available data from all patients will be used as detailed in this analysis plan. In addition, subjects may be too ill to perform assessments, such as the 6MWT or Borg, resulting in missing data for that assessment.

Methods for imputation and handling missing data, when applicable, will be described in the sections for the particular outcome.

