9.1.2 Primary Efficacy Analysis Data

The primary efficacy analysis will be based on all available measurements of the 6MWD for the FAS as observed in the study, with the exception that for subjects whose 6MWD measures at Week 6 or Week 12 of either Period are missing due to death or being too ill to perform 6MWT, the missing values will be imputed as the worst possible score (0 meter) and change-from-baseline scores calculated. For missing data due to any other reason, the missing value will not be imputed.

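### Protocol 6.3 allows removal from the study for noncompliance, against the follow-up policy elsewhere in the plan, so primary-endpoint walks may be lost needlessly

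*Protocol*

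**What the plan says.** Protocol 6.3 (Compliance) has sites ask about dosing at each visit and re-educate anyone who is noncompliant. It then adds: "Continued noncompliance may lead to withdrawal of the subject from the study, after consultation between the Investigator" and the sponsor's medical monitor or another sponsor representative.

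The passages on discontinuation say something different.

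- Protocol 7.5, on subjects who permanently stop drug early: "for any reason, the subject should be encouraged to remain in the study and complete all visits up to and including the ET Visit".
- Protocol 8.1, on what sites should encourage: "complete all study procedures and study visits as indicated by the study protocol, unless subjects provide written withdrawal of consent from the study".
- Protocol 8.1.1: "Subject discontinuation from study drug does not mean discontinuation from the study". The same section adds: "A positive pregnancy test will result in subject withdrawal from study drug, but the subject will be encouraged to continue participation in the study".
- Protocol 8.1.2, the section on leaving the study, describes only voluntary withdrawal of consent in writing.
- SAP 7.6 repeats the retention policy. Its reasons for not completing a treatment period are "death, lost to follow-up, study terminated by Sponsor, COVID-19 truncation, or withdrawal of consent". Noncompliance is not among them.

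On missing walks, SAP 9.1.2 assigns 0 m for death or being too ill to walk, and then states: "For missing data due to any other reason, the missing value will not be imputed".

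**The concern.** Section 6.3 treats poor adherence as a possible reason to end follow-up, whereas the rest of the plan treats stopping drug and leaving the study as separate events. The Full Analysis Population in Protocol 10.3 counts subjects as randomised whatever drug they were given. Removing people for how they took the drug works against that.

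The data at stake are primary-endpoint walks. Data already collected stay in the analysis, but later walks are never made. Actigraphy, the planned fallback when walks are missing (SAP 9.2), ends too. Adaptation 1 depends on the presence of both measures at Week 25, so one removed subject can count against both.

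Loss of this kind may be informative. Dosing is four times daily, titrated to 12 breaths, and Protocol 1.2.3 reports cough in 54% of the inhaled treprostinil group in the earlier PAH trial. A difference in adherence between treatments is therefore plausible, although the documents give no rate.

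**Working it through.** **1. The plan's own sample size.** Inputs (Protocol 10.2): difference 30 m, SD of differences 85 m, two-sided alpha 0.01, 124 evaluable. With SE = 85/√124 = 7.63 m, the noncentrality is 30/7.63 = 3.93 on 122 df, and power is 0.903. The smallest N reaching 90% is 123, so 124 reproduces. For the parallel design, 133 per arm with SD 75 m and alpha 0.05 gives power 0.904; 133/0.85 rounds up to 157 per arm, or 314. No figure in the plan is in dispute.

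**2. The rules side by side.**

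| Situation | Consequence | Source |
|---|---|---|
| Permanently stops drug, any reason | Encouraged to stay and complete visits | Protocol 7.5, 8.1.1; SAP 7.6 |
| Positive pregnancy test | Off drug, encouraged to stay | Protocol 8.1.1 |
| Withdraws consent in writing | Leaves study | Protocol 8.1.2 |
| Takes drug irregularly despite re-education | May be withdrawn from study | Protocol 6.3 |

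The last row has no counterpart in 8.1.2 or SAP 7.6. Section 7.5 describes an early termination (ET) visit for when a decision is made to end a subject's participation. No section says when noncompliance should lead to that decision.

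**3. Walks lost.** Crossover walks from randomisation onward are at Weeks 1, 6, 12, 14, 19 and 25, six in all; the Week 1 walk follows randomisation but precedes dosing. The key visits in SAP 9.2.1 are Weeks 1, 12, 14 and 25.

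- Crossover, removal just after Week 6: Weeks 12, 14, 19 and 25 are lost, 4 of 6 walks and 3 of 4 key visits.
- Crossover, removal just after Week 19: Week 25 is lost, 1 of 6 walks and 1 of 4 key visits.
- Parallel, removal after Week 6: Week 12 is lost, 1 of 2 key visits.

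**4. Whether the ET walk fills the gap.** Visit windows are ±3 days. Week 6 is days 39 to 45 and Week 12 is days 81 to 87. Days 46 to 80 (80 − 46 + 1 = 35 days) lie in neither. SAP 7 says "observations that do not fall within any predefined assessment window will be excluded from summaries", so an ET walk in that interval may not count as Week 12.

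**5. Discontinuation allowance.** Crossover: 136 − 124 = 12 subjects. Parallel: 314 − 266 = 48. Each removal uses one.

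**6. Power.** No removal rate is given, so extra losses beyond the planned 10% or 15% are assumed.

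| Extra loss | Crossover evaluable N | Power (alpha 0.01) | Parallel n per arm | Power (alpha 0.05) |
|---|---|---|---|---|
| 0% | 122 | 0.898 | 133 | 0.904 |
| 1% | 121 | 0.895 | 132 | 0.901 |
| 3% | 118 | 0.886 | 129 | 0.895 |
| 5% | 116 | 0.879 | 126 | 0.888 |
| 10% | 109 | 0.854 | 118 | 0.867 |

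The 0% crossover row is 136 × 0.90 = 122.4, rounded, not 124. At the crossover's alpha of 0.05, power stays at 0.955 or above throughout.

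**7. Bias, illustration only.** Shift = (fraction removed on active − fraction removed on placebo) × unobserved shortfall in walk distance. Assume a difference of 0 to 0.05 and a shortfall of 30 m in both arms. The shift is then 0 × 30 = 0 m to 0.05 × 30 = 1.5 m, at most 1.5/30 = 5% of the target effect. The sign reverses if placebo removals are more frequent. The shift is smaller if Week 6 data recover part of the shortfall. This is a two-arm, complete-case calculation and only a rough guide for the crossover.

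**The case against.** The strongest reply is that 6.3 addresses a different subject: one still prescribed drug who persistently fails to follow dosing, not one who has stopped. Removal is discretionary and comes after re-education and consultation. The other sections only encourage follow-up, and 7.5 foresees early termination by decision and asks for an ET visit with a walk. All this is true, and it makes removal less automatic. It does not explain why the irregular user should have weaker follow-up than the subject who takes nothing.

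Exposure is also limited. Everyone passes a 14 to 18 day active run-in, and those who cannot follow the regimen are not randomised. That stands, although the run-in uses 3 breaths and the target is 12. SAP 8.1.1 restates the re-education step without the withdrawal sentence, which helps but does not override the protocol.

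On missing data, SAP 9.1.4 promises crossover sensitivity analyses for the impact of missing values, and part of that section is redacted, so their absence cannot be claimed. The parallel design has a control-based imputation sensitivity analysis, which partly addresses the loss. A mixed model also uses observed Week 6 data.

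The window argument is the least certain. The exclusion in SAP 7 refers to summaries, SAP 9.1.2 uses all available walks, and the model specification is redacted. An ET walk may therefore enter the model in some form. Even so, it is one walk and replaces none of Period 2 if removal occurs in Period 1.

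These points limit the effect; they do not remove the conflict.

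**Conclusion.** The concern holds, as a minor one. Section 6.3 conflicts with the plan's own retention policy, and following it permits avoidable, possibly informative loss of primary-endpoint walks in an as-randomised analysis. Confidence is high for the conflict in the text. The effect on results cannot be sized from the documents: the number removed, the balance between treatments and the direction of bias are all unknown. The visit counts depend on when removal happens, and the 1.5 m figure rests on the assumed imbalance and shortfall. The power cost is small for an extra loss of a few percent.

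**What to change.** In Protocol 6.3, make the consequence of continued noncompliance withdrawal from study drug, with a reference to 8.1.1. Add that scheduled 6MWT, actigraphy and adverse event collection continue unless the subject withdraws consent under 8.1.2. Keep the permissive wording and the consultation step. Record the noncompliance as a protocol deviation so that it reaches the sponsor's pre-lock review in SAP 8.1.2.

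The cost is one sentence in an amendment, with no new scheduled visits. The downside is that poorly adherent subjects stay in the estimate, including crossover subjects followed off drug in Period 2. If 5% of subjects contributed no treatment contrast (an assumption), a 30 m effect would be diluted by 0.05 × 30 = 1.5 m, the same size as the illustrated bias. That dilution is what the Full Analysis Population definition and 8.1.1 already accept.

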#### 7 EXPERIMENTAL PROCEDURES

The allowable window for each study visit will be  $\pm 3$  days; however, where specified, the minimum Treatment or Washout Period must be adhered. Refer to Section 3.2 for the Overall Schedule of Times and Events.

#### 7.1 SCREENING PERIOD

# 7.1.1 Screening Visit 1 (Study Weeks -9 to -3)

All procedures may be conducted over a 6-week period to facilitate scheduling. The following assessments for Screening Visit 1 are required prior to dosing with study drug:

- Informed consent
- Demographics
- Medical history, including PH-COPD history
- PE
- Vital signs: height, weight, RR, HR, and BP (following at least 5 minutes of seated rest and collected prior to 6MWT); no other measurements or procedures should be performed during the rest period
- 12-lead ECG (following at least 5 minutes of rest)

- Blood draws for NT-proBNP and clinical laboratory parameters
- •
- Urine (prior to the first dose of study drug) and serum pregnancy tests for females of childbearing potential
- 6MWT and, if applicable, documentation of supplemental oxygen requirement
- Pulse oximetry (performed continuously prior to, during, and following the 6MWT)
- Borg dyspnea score immediately following the 6MWT
- PFTs (performed either before the 6MWT or after recovering from the 6MWT, if applicable)
- Chest CT scan; if performed within 6 months prior to the start of Screening Visit 1 a repeat assessment is not required. A redacted CT scan report should be provided to the Sponsor's Medical Monitor with the Pre-Baseline Review Form to confirm eligibility.
- Review inclusion/exclusion criteria
- RHC; an RHC obtained within 12 months prior to the start of Screening Visit 1 is acceptable for determining eligibility, even if done without oxygen or vasodilator challenge, and a repeat RHC is not required.

If all study eligibility criteria are met, dosing instructions and Tyvaso Inhalation device training will occur, followed by administration of study drug. The subject must remain at the study site for at least 1 hour after the first dose of study drug for observation. The following assessments should be completed after dosing:

- Assess for AEs
- Assess for changes in concomitant medications
- Issue the Sponsor-provided actigraphy, spirometry, and smart devices and provide training on use of the devices
- Subjects will be called weekly during the Screening Period and directed to call the study site coordinator or Investigator at any time to discuss study-related issues of concern (AEs, symptoms, tolerability, device issues, etc)

**Re-screening:** Subjects may be re-screened. The study-specific RHC performed during Screening Visit 1 is valid for up to 12 months and should not be repeated if the subject is being re-screened unless written approval is first obtained from the Sponsor's Medical Monitor.

#### 7.1.2 Screening Visit 2 (Study Week -2)

- PE
- Vital signs: weight, RR, HR, and BP (following at least 5 minutes of seated rest and collected prior to 6MWT); no other measurements or procedures should be performed during the rest period

- Blood draws for NT-proBNP and clinical laboratory parameters
- Collect study drug from subject and complete drug/device accountability
- Assess for AEs
- Assess for changes in concomitant medications
- Confirm study drug tolerability and compliance during the Screening Period
- Review inclusion/exclusion criteria and confirm study eligibility
- Complete the Pre-Baseline Review Form for Sponsor's Medical Monitor review and approval if subject tolerates drug and meets all other eligibility criteria
- Confirm proper use and capture of actigraphy data
- Confirm proper use and capture of spirometry data
- Subjects will be directed to call the study site coordinator or Investigator at any time to discuss study-related issues of concern (AEs, symptoms, tolerability, etc)

#### 7.2 WASHOUT PERIODS

### 7.2.1 (Study Week -1 and Study Week 13)

At the end of Screening Visit 2 (**Original Crossover Design** and **Contingent Parallel Design**) and Study Week 12 (**Original Crossover Design**), all subjects will enter a 7-day minimum (14 days maximum) Washout Period.

Subjects will be called mid-week following discharge from the site and directed to call the study site coordinator or Investigator at any time to discuss study-related issues of concern (AEs, concomitant medications, symptoms, tolerability, etc).

#### 7.3 TREATMENT PERIODS

# 7.3.1 Study Week 1 Visit (Baseline Visit)

The following baseline assessments must be performed prior to the first dose of study drug at the Study Week 1 Visit:

- QOL questionnaires: SGRQ and UCSD SOBQ
- PE
- Vital signs: weight, RR, HR, and BP (following at least 5 minutes of seated rest and collected prior to 6MWT); no other measurements or procedures should be performed during the rest period
- 12-lead ECG (following at least 5 minutes of rest)
- Blood draws for clinical laboratory parameters and NT-proBNP (NT-proBNP sample must be drawn prior to 6MWT)

•

- Reconfirm inclusion/exclusion criteria
- Confirm Sponsor's Medical Monitor approval to randomize subject
- Urine pregnancy test for females of childbearing potential
- Randomization using IRT
- PFTs (must be done after randomization either before the 6MWT or after recovery from the baseline 6MWT)
- 6MWT (conducted post randomization; following at least 10 minutes of seated rest) and, if applicable, documentation of supplemental oxygen requirement
- Pulse oximetry (performed continuously prior to, during, and following the 6MWT)
- Borg dyspnea score immediately following 6MWT
- Confirm proper use and capture of actigraphy data
- Confirm proper use and capture of spirometry data
- Collect PGA and provide training on at-home completion of the PGA

After the above assessments are completed, the following should be conducted:

- Provide and administer study drug, including dosing instructions
- Assess for AEs
- Assess for changes in concomitant medications
- Provide paper QOL questionnaires and training on at-home completion in the event telemedicine visits are needed
- Weekly telephone contact

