- b Vital signs and ECG must be performed after a 5-minute period of rest (seated rest for vital signs). No other procedures should be conducted during the rest period. When possible, vital signs should be collected prior to the 6MWT. Height will be measured and recorded only during Screening Visit 1.
- c Blood for the NT-proBNP assessment must be drawn prior to conducting the 6MWT and dosing of study drug during Screening Visit 1 and Study Weeks 1 & 14 in the **Original Crossover Design** or during Screening Visit 1 and Study Week 1 in the **Contingent Parallel Design**.
- d For females of childbearing potential. Urine (prior to the first dose of study drug) and serum pregnancy tests at Screening Visit 1 and a urine pregnancy test at Study Week 1. Serum pregnancy tests will be performed at all other scheduled visits.
- e The Screening Visit 1 6MWTs must precede open-label treprostinil dosing. The 6MWT at Study Week 1 must be performed after randomization, but before administration of study drug, and the 6MWT at Study Week 14 must be performed before administration of study drug. All other post-randomization 6MWTs will be performed between 10 and 60 minutes after study drug has been administered at the study site. Prior to the start of each 6MWT, the subject should rest (seated) for at least 10 minutes. Subjects receiving supplemental oxygen during any pre-randomization 6MWT must continue to receive the same flow rate at all subsequent 6MWT assessments. The supplemental oxygen flow rate must be recorded at each study visit, as applicable. If the site or subject has implemented protective measures against COVID-19, all subsequent 6MWT assessments should be made in a generally consistent manner.
- f Pulse oximetry to be performed continuously prior to, during, and following each 6MWT. Pulse oximetry will include the measurement of SpO2 and HR. The SpO2 and HR obtained immediately prior to and immediately following completion of the 6MWT will be recorded in the source documents and eCRF. The lowest recorded SpO2 obtained during each 6MWT (and associated HR) will be recorded in the source documents and eCRF.
- g See Appendix 15.2. The subject should be asked to rate their maximal breathlessness during the 6MWT.

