#### 4 SUBJECT ELIGIBILITY

# 4.1 INCLUSION CRITERIA

Subjects who meet the following criteria may be included in the study:

- 1. Voluntarily gives informed consent to participate in the study.
- 2. Males and females 18 years of age and above at the time of informed consent.
  - a. Females of childbearing potential (defined as less than 1 year postmenopausal and not surgically sterile) must agree to practice abstinence or use 2 highly effective methods of contraception (defined as a method of birth control that results in a less than 1% per year failure rate, such as approved hormonal contraceptives, barrier methods [condom or diaphragm] used with a spermicide, or an intrauterine device) for the duration of study treatment and for 48 hours after discontinuing study drug. Subjects must have negative pregnancy tests at Screening Visit 1 (urine [prior to the first dose of study drug] and serum) and the Baseline Visit (urine [Study Week 1]).
  - b. Males with a partner of childbearing potential must agree to use a barrier method (condom) with a spermicide for the duration of treatment and for at least 48 hours after discontinuing study drug.
- 3. Diagnosis of PH-COPD (WHO Group 3).
- 4. Clinical diagnosis of COPD per the Global Initiative for Chronic Obstructive Lung Disease (GOLD) diagnostic criteria (2020) and documented spirometry parameters measured during Screening Visit 1 (prior to start of low dose inhaled treprostinil), as follows:
  - a. FEV1 <80% predicted
  - b.  $FEV_1/FVC < 70$
- 5. Resting SpO2 ≥90% during Screening Visit 1, with or without supplemental oxygen, and supplemental oxygen cannot exceed 10 L/min by any mode of delivery.
- 6. A 6MWD ≥100 meters during Screening Visit 1 (prior to start of low dose inhaled treprostinil).

- 7. Willing to undergo RHC during Screening Visit 1. An RHC performed within 12 months prior to the start of Screening Visit 1 is acceptable for determining eligibility, even if done without oxygen or vasodilator challenge, and a repeat RHC is not required. The following parameters must be documented for eligibility:
  - a. PVR >4 Wood units
  - b. Pulmonary artery wedge pressure (PAWP) or left ventricular end-diastolic pressure (LVEDP) of ≤15 mmHg
  - c. PAPm of ≥30 mmHg
- Must be on a stable and optimized dose of chronic COPD medications for ≥30 days prior
  to the start of Screening Visit 1 and remain on the same dose throughout the Screening
  Period.

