7.1 BASELINE

Given the crossover design utilized for this study, Periods 1 and 2 each have a different baseline for efficacy measurements: Period 1: Day 1 and Period 2: Week 14. With the exception of actigraphy measurements, the baseline value will be defined as the non-missing value immediately prior to dosing with study drug for Period 1: Day 1 and Period 2: Week 14. The baseline period for actigraphy measurements will be the last 7 days during the washout period prior to the day of dosing on Day 1 and Week 14. In the event that the washout period is less than 7 days then only the non-dosing days will be used to derive a baseline average.

For safety evaluations, the baseline will be defined as the last evaluation closest, but prior to, the first dose of study drug during the low dose run-in period.

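### The Week 1 walk that serves as the primary baseline is scheduled after randomization, so a failed walk leaves an avoidable randomized subject without a Day 1 baseline; the loss is small

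*Protocol*

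**What the plan says.** Protocol 7.3.1 lists the Week 1 procedures in order. "Randomization using IRT" comes before the walk, and the walk entry reads "6MWT (conducted post randomization; following at least 10 minutes of seated rest". Footnote e of Table 3-1 states the same sequence as a requirement: "The 6MWT at Study Week 1 must be performed after randomization, but before administration of study drug". Footnote e of Table 3-2 repeats it for the Contingent Parallel Design. The order is therefore deliberate. The readable text gives no reason for it and does not make a completed Week 1 walk a condition of randomizing.

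Protocol 7.3.1 also puts the walk among the assessments that come before the first dose, and provides study drug only once those assessments are finished.

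The only earlier walk is at Screening Visit 1: "The Screening Visit 1 6MWTs must precede open-label treprostinil dosing". There is none at Screening Visit 2. The distance criterion for entry uses the screening walk alone: "A 6MWD ≥100 meters during Screening Visit 1 (prior to start of low dose inhaled treprostinil".

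SAP 7.1 says that, actigraphy aside, "the baseline value will be defined as the non-missing value immediately prior to dosing with study drug", and ties this to Day 1 for Period 1 and to Week 14 for Period 2. SAP 12.4.3 keeps only the Day 1 baseline in the parallel design. SAP 7.4 and 12.4.4 enter baseline as a continuous covariate. Protocol 10.3 defines the Full Analysis Population as randomized subjects who received at least one dose.

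**The concern.** Randomization normally comes as late as possible, once everything needed to analyse the subject is in hand. Here the measurement that the primary change score depends on is taken after the allocation has been used. If the walk is not done on the day (the subject is unwell, the test is abandoned, or the test is invalid), the subject already counts as randomized.

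Two things can then happen. The subject is not dosed and falls outside the Full Analysis Population, which makes that set depart from the set as randomized. Or the subject is dosed without a walk and enters the analysis set with no Day 1 baseline. SAP 9.1.2 offers no rescue: its 0 m value covers only death or being too ill at Weeks 6 and 12, and even then a baseline is needed to form a change. Neither outcome can arise from a missing Week 1 walk if the walk precedes randomization. What is at stake is some precision and a clean analysis set, not the direction of the result.

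**Working it through.** **1. What a missing Week 1 walk does**

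| Case | Parallel design | Crossover design |
|---|---|---|
| Randomized, not dosed (follows from 7.3.1) | Outside the Full Analysis Population | Outside the Full Analysis Population |
| Dosed without the walk (a deviation from 7.3.1) | No change score at Week 6 or 12 | Period 1 changes and the within-subject contrast are lost; Period 2 keeps its Week 14 baseline |

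**2. Inputs**

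Protocol 10.2 and SAP 5.1:
- Crossover: difference 30 m, SD of differences 85 m, two-sided alpha 0.01, N = 124 (62 per sequence), about 136 after a 10% allowance.
- Parallel: difference 30 m, SD 75 m, two-sided alpha 0.05, 133 per arm, about 314 after a 15% allowance.

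SAP 7: final tests in the crossover are at 0.05, or at 0.022 if the interim efficacy analysis is run.

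**3. The plan's own figures**

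Power is the probability that a noncentral t variable exceeds the two-sided critical value.
- Crossover: noncentrality = 30 × √124 / 85 = 3.93 on 122 df. Power at 0.01 is 90.3%, against 90% stated.
- Parallel: noncentrality = 30 / (75 × √(2/133)) = 3.26 on 264 df. Power at 0.05 is 90.1%, against at least 90% stated.
- Allowances: 124/0.90 = 137.8 against about 136; 266/0.85 = 312.9 against about 314.
- SAP 9.2.1 says about 88 subjects give 90% power at 0.05 in the crossover. The same formula gives 90.6%.

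The stated sample sizes reproduce.

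**4. Effect of failed Week 1 walks**

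The documents give no failure rate. Assume 1% to 5%. That is 1.4 to 6.8 of 136 randomized subjects, or 3.1 to 15.7 of 314.

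Take the same fraction off the evaluable numbers and treat each such subject as wholly lost: 124 becomes 122.8 (1%) or 117.8 (5%), and 133 per arm becomes 131.7 or 126.3.

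| Test | No loss | 1% lost | 5% lost |
|---|---|---|---|
| Parallel, 0.05 | 90.1% | 89.9% | 88.6% |
| Crossover, 0.05 (final, no interim) | 97.4% | 97.3% | 96.7% |
| Crossover, 0.022 (final, after interim) | 94.5% | 94.3% | 93.3% |
| Crossover, 0.01 (sizing level only) | 90.3% | 90.0% | 88.5% |

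These losses are upper bounds for two reasons. They assume that the discontinuation allowance is already fully used by other causes, although a subject who leaves undosed could reasonably be counted within it. In the crossover they also ignore the Period 2 data that a dosed subject would still contribute.

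**The case against.** The strongest reply is that the plan already guards against the worse case. Section 7.3.1 requires the walk before dosing, so a subject dosed without one is a deviation. That stands, and it makes the undosed, post-randomization exclusion the main consequence.

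A reader might infer that the SAP would fall back on the Screening Visit 1 walk, mixing pre-run-in and post-washout baselines. The documents do not support this as the natural reading. SAP 7.1 names Day 1. SAP 7.5 and 8.3.2 list the 6MWD baseline as Day 1 only, while SAP 8.3.2 gives FEV1 at Screening Visit 1 and Day 1. SAP 9.2.1 counts 6MWD presence at Week 1 itself. A last-value-before-dosing wording is used only for safety.

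A reader might also infer that affected crossover subjects leave the primary analysis altogether. A dosed subject does not, because Period 2 has its own baseline and SAP 9.1.2 uses all available walks.

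Other points on that side carry some weight. The randomization visit must be onsite and entry requires a screening walk of at least 100 m, so failures should be few. Visit windows of 3 days either way and a washout of up to 14 days might let a site repeat the walk before dosing under the present order, though no readable text provides for it. The sentence "Subjects who are not retained will not be replaced during the study" concerns retention, so it does not settle how a failed baseline is treated. The model details in SAP 9.1.3 are redacted and most of SAP Section 6 is not readable; either could hold a baseline rule.

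Finally, with the walk first, staff would see the baseline before randomizing and might select or repeat. Such selection happens before allocation and under the blind, so it does not bias the comparison, and a check without a distance threshold gives little incentive to influence effort.

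**Conclusion.** The point holds as a minor design weakness. The order is mandatory and unexplained, and it creates avoidable randomized subjects without a Day 1 baseline. The cost is some precision and, mainly, exclusions from the analysis set after randomization. Because the walk precedes the first blinded dose, its absence should not depend on treatment, and no directional bias is expected while the blind holds.

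At an assumed 5% failure rate with complete loss, the power cost is about 1.5 points in the parallel design. In the crossover it is about 0.7 points at 0.05 or 1.2 points at 0.022. At 1% it is about 0.3 points or less in each case.

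A reader might conclude from the 90.3% sizing figure that the crossover has almost no power to spare. That does not follow: 0.01 is the level used to size the trial, while the final test is at 0.05 or 0.022, where 124 subjects give 97.4% or 94.5%. The parallel design does sit close to 90%.

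The PFTs are also placed after randomization, but that does not affect the primary analysis. The size of the problem rests wholly on the assumed failure rate.

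**What to change.** In Protocol 7.3.1 and in footnote e of Tables 3-1 and 3-2, place the IRT randomization after the baseline 6MWT with its oximetry and Borg score, and before study drug is provided. Have the IRT ask for confirmation that a Week 1 6MWT was completed, with no distance threshold. State that a failed walk may be repeated within the existing visit window and washout limits before randomization.

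The cost is a change of order within one visit and one added IRT field. The drawback is that a few subjects will complete baseline tests and not be randomized that day. Sample size, visit schedule and analysis model are unchanged.
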